6.3 Definition of Baseline and Postbaseline Periods

For efficacy analyses (excluding daily diaries), baseline is defined as the last non-missing value prior to the first dose of study drug, unless otherwise specified. In most cases, this will be the measurement recorded at Week 0 (Visit 2).

Baseline for the safety analyses is defined as:

- The last non-missing scheduled (planned) measurement prior to the first dose of the study drug for continuous measures by-visit analyses, and
- All non-missing measurements prior to the first dose of the study drug for all other analyses.

In general, for efficacy and safety (except adverse events) analyses, when the baseline measurement is collected on the same day (where time is not collected) as the first dose date, this measurement will be used as the baseline value for data analysis.

Postbaseline measures for the safety analyses are defined as the non-missing scheduled (planned) measurements after the first dose of the study drug for continuous measures by-visit analyses and all non-missing measurements after the first dose of the study drug for all other analyses.

Postbaseline data collection begins after the first dose of study drug administration at Visit 2 (Week 0) and will continue through Visit 16 (Week 52), early study termination visit, or the follow-up visit.

The baseline value for the daily diary assessments (Worst Pain Numeric Rating Scale [NRS], Worst Joint Pain NRS, Worst Fatigue NRS, Joint Stiffness Duration, Joint Stiffness Severity NRS, and Patient Global Impression of Severity [PGI-S]) is defined as the average of the non-missing assessments in the last 7 days prior to the date of first study drug administration (expected at Week 0, Visit 2). There must be at least 4 non-missing daily measurements in the 7 days indicated. If there are less than 4 non-missing daily assessments collected prior to the date of first study drug administration, then the baseline value will be designated as missing. If there are multiple assessments collected on the same day, only the first collected record will be used.

Postbaseline values of daily diary assessments collected after first study drug administration through Visit 16, or early study termination visit, will be defined as the average of the last 7 days prior to the date of the study visit. If less than 4 non-missing daily measurements are present, the visit will be set to missing.

Protocol-defined visit windows are defined as ± 3 days for Visit 3 (Week 1) and ± 4 days, from Visit 4 (Week 4) until Visit 16 (Week 52). If there is data within the protocol-defined window, that data will be used in by-visit analyses. If a protocol-defined visit is missing, then the nearest unscheduled visit data that exists will be mapped to that visit and included in by-visit analyses. If 2 unscheduled visits are equidistant to a missing visit, the earlier unscheduled visit will be used.

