To evaluate the effect of baricitinib 4-mg QD and background SoC therapy compared to placebo and SoC on SLE disease activity	
 • Proportion of patients achieving an SRI-4 response at Week 52, defined as: 
 • a reduction of ≥ 4 points from baseline in SLEDAI-2K score, and • No new BILAG A and no more than 1 new BILAG B disease activity score, and • No worsening (defined as an increase of ≥ 0.3 points [10 mm] from baseline) in the PGA of Disease Activity.
Major Secondary^c	
To evaluate the effect of baricitinib 4-mg QD plus SoC compared to placebo plus SoC on SLE disease activity	
 • Proportion of patients achieving an SRI-4 response at Week 24 • Proportion of patients achieving a LLDAS response at Week 52
To evaluate the corticosteroid sparing effect of baricitinib 4-mg QD plus SoC compared to placebo plus SoC	
 • Proportion of patients receiving >7.5 mg prednisone (or equivalent) at baseline able to decrease dose by $\geq 25\%$ to a prednisone equivalent dose of ≤ 7.5 mg/day maintained between Week 40 and Week 52
To evaluate the effect of baricitinib 4-mg QD plus SoC compared to placebo plus SoC on SLE flares	
 • Time to first severe flare over 52 weeks
To evaluate the effect of baricitinib 4-mg QD plus SoC compared to placebo plus SoC on PROs	
 • Change from baseline in Worst Pain NRS at Week 52 • Change from baseline in FACIT-Fatigue total score at Week 52

Primary and Major Secondary Objectives and Endpoints

Objectives	Endpoints (Variables)^a
To evaluate the effect of baricitinib 2-mg QD plus SoC compared to placebo plus SoC on SLE disease activity	
 • Proportion of patients achieving an SRI-4 response at Week 52 • Proportion of patients achieving an SRI-4 response at Week 24 • Proportion of patients achieving a LLDAS response at Week 52
To evaluate the corticosteroid sparing effect of baricitinib 2-mg QD plus SoC compared to placebo plus SoC	
 • Proportion of patients receiving >7.5 mg prednisone (or equivalent) at baseline able to decrease dose by $\geq 25\%$ to a prednisone equivalent dose of ≤ 7.5 mg/day maintained between Week 40 and Week 52

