6.2 Definition of Populations

Analysis populations are defined in [Table JAIA.6.1](#) along with their associated purpose. The treatment groups and inferential comparisons described in this table will be used unless otherwise specified. Also, unless otherwise specified patients will be analyzed according to the treatment to which they were assigned.

Table JAIA.6.1. Analysis Populations

Population	Description
Screened Population	
Definition: Includes all patients who signed informed consent form.
 
Purpose: Used for summarizing screen failures and reason for screen failures.
 
Treatment Groups: None
 
Inferential Comparisons: None

Randomized Population	
Definition: Includes all randomized patients.
 
Purpose: Used for listing patient disposition and treatment assignment.
 
Treatment Groups: baricitinib 2-mg QD, baricitinib 4-mg QD, placebo QD
 
Inferential Comparisons: None

mITT Population	
Definition: All randomized patients who receive at least 1 dose of study treatment (regardless of if the patient does not receive the correct treatment, or otherwise does not follow the protocol).
 
Purpose: Used for efficacy and health outcomes related analyses.
 
Treatment Groups: baricitinib 2-mg QD, baricitinib 4-mg QD, placebo QD
 
Inferential Comparisons: baricitinib 4-mg QD vs. placebo QD; baricitinib 2-mg QD vs. placebo QD

Per Protocol Population	
Definition: All randomized patients who received at least 1 dose of study treatment without important protocol deviations that impacted the analysis (defined in a separate study deviation rules document).
 
Purpose: Used for the sensitivity analysis for the primary efficacy.
 
Treatment Groups: baricitinib 2-mg QD, baricitinib 4-mg QD, placebo QD
 
Inferential Comparisons: baricitinib 4-mg QD vs. placebo QD; baricitinib 2-mg QD vs. placebo QD

Safety Population	
Definition: The safety population is defined as all randomized patients who receive at least 1 dose of investigational product and who did not discontinue from the study for the reason “Lost to follow-up” at the first postbaseline visit.
 
Purpose: Used for all safety analyses.
 
Treatment Groups: baricitinib 2-mg QD, baricitinib 4-mg QD, placebo QD
 
Inferential Comparisons: baricitinib 4-mg QD vs. placebo QD; baricitinib 2-mg QD vs. placebo QD

Abbreviations: mITT = modified intent-to-treat; QD = once daily.

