Treatment comparisons of continuous efficacy and health outcome variables, except for SLICC/ACR Damage Index, Patient's Global Impression of Change and Joint Stiffness Duration, will use a restricted maximum likelihood-based MMRM analysis. The model will include the following explanatory variables as fixed factors: treatment, baseline disease activity (total SLEDAI-2K <10; ≥ 10), baseline corticosteroid dose (<10 mg/day; ≥ 10 mg/day prednisone or equivalent), region (North America, Central/South America/Mexico, Europe, Asia and Rest of World), visit (as categorical variable), baseline value, treatment-by-visit interaction, and baseline value-by-visit interaction. The response variable will be change from baseline across postbaseline visits. Within-patient errors will be modeled using an unstructured covariance structure. If the model fails to converge, the following covariance structures will be implemented in the following order: heterogeneous Toeplitz, heterogeneous autoregressive (1) heterogeneous compound symmetry, and autoregressive. The least squares (LS mean) difference, standard error, p-value, and CIs will be reported. Type III tests for the LS means will be used for the statistical comparisons.

Treatment comparisons of SLICC/ACR Damage Index will be made using analysis of covariance (ANCOVA) with baseline value as covariate. For Patient's Global Impression of Change, the analysis of variance (ANOVA) will be applied. For both models, treatment, baseline disease activity (total SLEDAI-2K <10; ≥ 10), baseline corticosteroid dose (<10 mg/day; ≥ 10 mg/day prednisone or equivalent), and region (North America, Central/South America/Mexico, Europe,

Asia and Rest of World) will be included as the categorical factors. Type III tests for LS means will be used for statistical comparison between treatment groups. The LS mean difference, standard error, p-value, and 95% CI may also be reported.

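### A missing diary baseline removes a patient from the Worst Pain NRS MMRM at every visit, at a modest and avoidable cost in precision

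*SAP*

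**What the plan says.** Section 6.3 gives the daily diary measures their own baseline rule. The general rule leaves them out: "For efficacy analyses (excluding daily diaries), baseline is defined as the last non-missing value prior to the first dose of study drug". For diaries, baseline is the "average of the non-missing assessments in the last 7 days prior to the date of first study drug administration". A minimum applies: "There must be at least 4 non-missing daily measurements in the 7 days indicated". With fewer than 4, "then the baseline value will be designated as missing". No wider window, earlier block of days or imputed value is offered.

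Section 6.4 defines the MMRM used for nearly all continuous endpoints: "The response variable will be change from baseline across postbaseline visits". Its fixed effects include "baseline value, treatment-by-visit interaction, and baseline value-by-visit interaction".

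Table JAIA.4.1 lists "Change from baseline in Worst Pain NRS at Week 52" as a major secondary endpoint for 4 mg and again for 2 mg. Table JAIA.6.6 assigns it MMRM with multiple imputation on the PPCV datapoint set for principal inference, and plain MMRM on PP and AC as supplemental analyses. Worst Fatigue, Worst Joint Pain, Joint Stiffness Severity and Patient Global Impression of Severity are diary measures analysed by MMRM on PP.

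Efficacy analyses use the mITT population of Table JAIA.6.1: "All randomized patients who receive at least 1 dose of study treatment", whether or not they then followed the protocol.

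**The concern.** Each rule is ordinary alone. Together they act as a complete-case deletion that the SAP does not mention. Without a baseline, both the response and a covariate are undefined at every visit, so the patient leaves the model however full the postbaseline diary is. Outcome data already collected on a multiplicity-controlled endpoint are discarded because of a pre-treatment diary lapse.

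The footnotes to Table JAIA.6.6 name a subset of mITT wherever one is intended (SRI-x, organ domains, CLASI, steroid sparing, WPAI). Worst Pain NRS has none, so a reader of the table would expect all mITT patients to inform that result.

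**Working it through.** **Step 1. The plan's own power figure.** Section 5.2 states more than 90% power for SRI-4, 40% against 57%, with about 750 patients randomized 1:1:1, so 250 per arm, at 2-sided alpha 0.05. The pooled chi-square calculation gives 96.9%, consistent with the statement. The SAP gives no effect size, SD or power for Worst Pain NRS, so nothing there can be reproduced for this endpoint.

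**Step 2. Does any other rule bring these patients back?**
- *Hybrid imputation (6.4.2.4).* Imputed values are kept only where the data are missing because of COVID-19. Step 3 of that algorithm resets the rest to missing before the MMRM. A COVID-related baseline lapse might be retained under PPCV, but the SAP does not say that baselines are imputed. PP and AC have no such route.
- *mLOCF (6.4.2.3).* It serves the ANCOVA and Wilcoxon analyses and carries postbaseline values forward.
- *NRI (6.4.2.1).* It applies to responder endpoints.
- *Missing at random under MMRM (6.4.2.2).* This covers missing outcomes, not a missing covariate.

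So a lapse unrelated to COVID-19 leads to exclusion. The Section 6.3 sentence that sets baseline to missing does not repeat the 7-day window; I read it together with the sentence before it. As a mechanical check, in a simulated set of 300 patients with 4 visits and 25 missing baselines, all 1,200 postbaseline values were observed. The change-from-baseline model could use 1,100 rows from 275 patients.

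**Step 3. Which endpoints?** Worst Pain NRS is the only major secondary affected, because FACIT-Fatigue is not in Section 6.3's list of diary measures. The four other MMRM diary endpoints named above are also affected. Joint Stiffness Duration uses a Wilcoxon test. Its change is equally undefined without a baseline, but it lies outside the MMRM point made here.

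**Step 4. Size of the loss.** Let f be the fraction without a baseline. It is assumed, since the SAP gives no rate.

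SE factor = 1/√(1 − f). Power = Φ[(z + 1.96)·√(1 − f) − 1.96], with z = 1.282 for an assumed 90% power and z = 0.842 for an assumed 80%.

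| f (assumed) | SE factor | from 90% | from 80% |
|---|---|---|---|
| 2% | 1.010 | 89.4% | 79.2% |
| 5% | 1.026 | 88.5% | 78.0% |
| 10% | 1.054 | 86.8% | 75.7% |

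Worked line at 10%: 3.242 × 0.9487 − 1.96 = 1.115, and Φ(1.115) = 86.8%.

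**Step 5. What can be recovered?** Let r be the assumed correlation between baseline and outcome. A patient with a baseline has residual variance proportional to 1 − r²; one without has 1. Kept in a model that treats baseline as a response, the second patient therefore carries about 1 − r² of the information of the first: 75% at r = 0.5 and 51% at r = 0.7. With f = 10%, effective information is 0.9 + 0.1 × 0.75 = 0.975, or 0.9 + 0.1 × 0.51 = 0.951. The SE factor is then 1/√0.975 = 1.013 or 1/√0.951 = 1.025, against 1.054 under exclusion.

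Pooled-mean imputation does worse. With f = 10%, one postbaseline visit and equal weighting, its relative variance is 0.9 + 0.1/(1 − r²), against 1/0.9 = 1.111 for exclusion.
- r = 0.5: 1.033, so (1.111 − 1.033)/0.111 = about 70% of the loss is recovered.
- r = 0.7: 1.096, about 14% recovered.
- Break-even: 0.1/(1 − r²) = 0.211, so r is about 0.73. Above that, imputing the mean is worse than exclusion.

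**The case against.** The strongest defence is that nothing here is misstated. The 4-of-7 threshold is explicit, it is also applied after baseline, and analysing change in patients who have a baseline is common practice. That stands: the threshold itself is not an error. The gap is what follows from it without being said.

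A reader might infer that the treatment comparison is biased. The SAP does not support this. Randomization and the expected first dose are both at Visit 2, so exclusion depends on diary days before dosing and cannot depend on a response to treatment. The comparison among included patients remains randomized.

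A reader might also infer that the SAP contradicts its own mITT definition. That goes too far. The definition sets who is eligible, and lacking data that a model needs does not rewrite it. What can be said is that the analysed set is smaller than mITT and that Table JAIA.6.6 does not show it.

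The size is also open to challenge. All rates above are assumed, and at 2% the effect is negligible. Diary completion may have been enforced before randomization in the protocol, which is not at hand, so the affected group could be close to empty. Nor will every such patient supply useful outcomes, since each visit again needs 4 of 7 days. These points limit the gain but do not justify discarding the outcomes that are usable.

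**Conclusion.** The point holds in limited form. Under Sections 6.3 and 6.4, a diary lapse before first dose, for reasons other than COVID-19, removes the patient from the Worst Pain NRS MMRM and from the four other MMRM diary endpoints. Under PPCV, the fate of a COVID-related lapse is not stated. The harm is precision: an SE increase of 1.0% to 5.4% over assumed missing rates of 2% to 10%, or a fall from an assumed 90% power of between 0.6 and 3.2 points. These figures rest on assumed rates and assumed starting power, and on the excluded patients otherwise having data like the rest. It is worth correcting because the endpoint is multiplicity-controlled, the change is cheap, and the supplemental PP and AC analyses share the same baseline rule and so cannot reveal the effect.

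**What to change.** For the diary MMRM endpoints, use a constrained longitudinal model. The diary score is the response at baseline and at each postbaseline visit, with one baseline mean common to all arms, treatment effects at postbaseline visits only, and the stratification factors retained. Baseline and baseline-by-visit then leave the covariate list. Because the baseline mean is shared, the Week 52 treatment difference is still the difference in change from baseline, and any patient with a usable diary value stays in.

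Do not substitute simple pooled-mean imputation, which recovers little or nothing when baseline and outcome are strongly correlated. State whether a baseline missing because of COVID-19 is imputed under PPCV. Report the number without a diary baseline by arm.

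The cost is a small change of model form, a few lines of SAP wording, and one more time point in the covariance matrix. Patients without a baseline still contribute less than those with one.

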5.1 Summary of Study Design

Study I4V-MC-JAIA (JAIA) is a Phase 3, multicenter, randomized, double-blind, parallel-group, placebo-controlled, outpatient, 52-week study evaluating the efficacy and safety of baricitinib 4-mg and 2-mg in patients with systemic lupus erythematosus (SLE) receiving standard therapy. The study has a screening period followed by a 52-week double-blinded treatment period and a 4-week post-treatment follow-up period.

Patients will be randomized in a 1:1:1 ratio between baricitinib 4-mg, 2-mg, and placebo. Study treatment will be administered as 2-mg and 4-mg tablets once daily (QD). Patients with documented renal impairment (defined as screening estimated glomerular filtration rate [eGFR] ≥ 40 to < 60 mL/min/1.73 m²), who are randomized to active treatment (either to the baricitinib 4-mg arm or the baricitinib 2-mg arm) will receive a baricitinib 2-mg QD dose by the interactive web-response system (IWRS).

Investigators are encouraged to taper corticosteroids according to clinical practice with a goal of ≤ 7.5 mg/day by Week 40. A single corticosteroid burst is permitted for patients with increased disease activity early in the treatment period. Complete details of corticosteroid rules in relation to the clinical trial endpoints can be found in JAIA Protocol (b) Section 7.7.1.

Patients who were unable to attend Visit 16 within the original protocol-defined window (Week 52/Day 365 \pm 4 days) due to COVID-19 were permitted to delay completion of the Visit 16 by up to 1 month. Patients who complete treatment in this study through Visit 16 may be eligible to participate in a study extension, if enrollment criteria are met.

[figure not shown]

Figure JAIA.5.1.

Illustrates the study design.

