
Description and Derivation of Efficacy/Health Outcomes Measures and Endpoints

Measure	Description	Variable	Derivation/Comment	Definition of Missing
Tender/Swollen Joint Count (28 Joints)	28 joints are assessed as tender only, swollen only, tender and swollen, not evaluable.	Tender Joint Count 28/ Swollen Joint Count 28	The number of tender and swollen joints will be calculated by summing all joints respectively. Other rules apply. (See Appendix 4).	For patients who have an incomplete set of joints evaluated, the joint count will be adjusted to a 28-joint count for tenderness and a 28-joint count for swelling by dividing the number of affected joints by the number of evaluated joints and multiplying by 28.
SLICC/ACR	SLICC/ACR Damage Index assesses damage to 12 organ systems regardless of its cause.	SLICC/ACR Damage Index Score	Calculated as the sum of all available entries with a maximum score of 47.	“Missing” item is coded as 0.
Worst Pain NRS	This Worst Pain NRS is a single-item patient-administered 11-point horizontal scale anchored at 0 (no pain) and 10 (pain as bad as you can imagine).	Worst Pain NRS score	Calculated by averaging data for all available daily diary entries for a 7-day period prior to the visit, not inclusive of the clinic visit day	Missing if fewer than 4 available daily measurements in the relevant 7 days
FACIT-Fatigue	The FACIT-Fatigue scale (Cella and Webster 1997) is a 13-item symptom-specific questionnaire that assesses self-reported severity of fatigue and its impact upon daily activities and functioning.	Facit-Fatigue total score	The FACIT-Fatigue uses 0 (“not at all”) to 4 (“very much”) numeric rating scales to assess fatigue and its impact in the past 7 days. Scores range from 0 to 52 with higher scores indicating less fatigue. The FACIT-Fatigue Scoring Guidelines (Version 4) will be used to calculate the Total Score. Reversals are needed for all items except An5 and An7, as described in scoring manual. http://www.ser.es/wp-content/uploads/2015/03/FACIT-F_INDICE.pdf .	Missing items are acceptable as long as more than 50% of the items are answered (that is, a minimum of 7 out of 13 items), the sum of available items will be multiplied by 13, then divided by the number of items answered to obtain the total score. If less than 7 items are answered, the FACIT-Fatigue total score will be set to missing.

Description and Derivation of Efficacy/Health Outcomes Measures and Endpoints

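### When a scheduled visit is missed, diary entries recorded around the target day have no route into the Worst Pain NRS analysis

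*SAP*

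**What the plan says.** Section 6.3 defines each postbaseline diary value by the visit date: it "will be defined as the average of the last 7 days prior to the date of the study visit". The minimum-data rule follows: "If less than 4 non-missing daily measurements are present, the visit will be set to missing". Table JAIA.6.4 gives the same derivation for Worst Pain NRS: "Calculated by averaging data for all available daily diary entries for a 7-day period prior to the visit, not inclusive of the clinic visit day". The baseline diary value has a different anchor, the first dose: "average of the non-missing assessments in the last 7 days prior to the date of first study drug administration".

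For a visit that did not happen, Section 6.3 has one general fallback: "If a protocol-defined visit is missing, then the nearest unscheduled visit data that exists will be mapped to that visit". It sets no maximum distance and does not mention diaries.

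Section 6.4.2.4 sends data missing because of COVID-19 to multiple imputation and leaves other missing continuous data to the MMRM. Table JAIA.6.6 makes MMRM+MI on the PPCV datapoint set the principal inference for Worst Pain NRS at Week 52. Section 5.1 adds that patients unable to attend Visit 16 in its window "due to COVID-19 were permitted to delay completion of the Visit 16 by up to 1 month".

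**The concern.** A daily diary does not depend on attending the clinic on a given day. A patient who missed Visit 16 may still have recorded at least 4 of the 7 days before Day 365. Under the stated derivation those entries cannot become a Week 52 value, because there is no visit date to count back from. The value is then modelled, or it is borrowed from whatever unscheduled visit lies nearest.

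Modelling relies on a missing-at-random assumption that is unnecessary where the measurement exists. Borrowing can put a different week under the Week 52 label. Both would occur where the pandemic removed visits, on an endpoint that carries confirmatory alpha. The same applies to the other diary scores in Section 6.3: Worst Joint Pain, Worst Fatigue, Joint Stiffness Duration, Joint Stiffness Severity and Patient Global Impression of Severity.

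Section 6.4.2.4 also fits this case poorly. It describes COVID-19 missing data as data not collected, or collected while the patient was off drug. Entries recorded on drug around a missed visit are neither.

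**Working it through.** **The plan's own figure.** The only power statement (Section 5.2) is for SRI-4: more than 90% for 40% vs 57%, 250 per arm (750/3), two-sided 0.05. The pooled rate is 0.485, so the null SE is √(2×0.485×0.515/250) = 0.0447. The alternative SE is √((0.40×0.60+0.57×0.43)/250) = 0.0441. Then z = (0.17 − 1.96×0.0447)/0.0441 ≈ 1.87, which gives 96.9%. The statement holds but does not bear on this point. The SAP states no power or standard deviation for Worst Pain NRS.

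**Which days are used.** Section 5.1 puts Week 52 at Day 365 ± 4. The 7 days before Day 365 are Days 358-364. A visit on day v uses days v−7 to v−1, so the overlap with Days 358-364 is max(0, 7 − |v − 365|) days.

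| Anchor for the Week 52 value | Diary days used | Overlap with 358-364 |
|---|---|---|
| Visit on Day 365 | 358-364 | 7 of 7 |
| Visit at −4 or +4 days | 354-360 or 362-368 | 3 of 7 |
| Missed visit, unscheduled visit Day 358 | 351-357 | 0 of 7 |
| Missed visit, unscheduled visit Day 350 | 343-349 | 0 of 7 |
| Missed visit, no unscheduled visit | none | imputed |
| Visit 16 delayed 7 days | 365-371 | 0 of 7 |
| Visit 16 delayed 30 days | 388-394 | 0 of 7 |

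Any unscheduled visit 7 or more days from Day 365 therefore supplies none of the target week, even if that week's diary is complete.

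**Precision.** The SAP gives neither the share f of Week 52 visits missed with usable diaries nor the correlation ρ between successive visits. Both are assumptions here. With two visits and a likelihood analysis, the variance of the Week 52 mean is (σ²/n)×[1 + (f/(1−f))(1−ρ²)]. Using the recorded values restores σ²/n, so the SE falls by 1 − 1/√[1 + (f/(1−f))(1−ρ²)].

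| f | ρ = 0.5 | ρ = 0.7 | ρ = 0.85 |
|---|---|---|---|
| 3% | 1.1% | 0.8% | 0.4% |
| 5% | 1.9% | 1.3% | 0.7% |
| 10% | 3.9% | 2.7% | 1.5% |

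Worked case, f = 10% and ρ = 0.7: (0.10/0.90)×0.51 = 0.0567, and 1 − 1/√1.0567 = 2.7%.

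A repeated-measures simulation with 250 per arm gave SEs of 0.2058, 0.2062 and 0.2063 with the diaries used, against 0.2075, 0.2090 and 0.2120 for direct MMRM, at f = 3%, 5% and 10%. The reductions are 0.8%, 1.3% and 2.7%, in line with the ρ = 0.7 column.

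**The case against.** Several parts of the case against stand.

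- **A missed visit does not always leave the score missing.** The unscheduled-visit mapping can supply an anchor. It is a weak one, with no distance limit, but any new rule must say which of the two comes first.
- **The SAP does not say that diary entries are discarded.** A reader might infer a plan to throw data away. The text supports only that no rule brings these entries in, and the COVID-19 wording leaves their treatment unclear.
- **A delayed Visit 16 is not shown to be an error.** A reader might conclude that the score then comes from the wrong weeks, since a 30-day delay uses Days 388-394. But the same patient's SRI-4 and FACIT-Fatigue are also taken at the delayed visit, and the visit-date rule keeps pain aligned with them. Either alignment can be defended. The worry that drug assigned through Week 48 had run out is speculative, because the SAP does not give supply length. PPCV also already treats COVID-19 off-drug interruptions of 20 days or more as missing.
- **A larger precision gain does not belong to this point.** Against imputation followed by MMRM, the same simulation gave SEs of 0.2146, 0.2211 and 0.2353, which would suggest gains of about 4%, 7% and 12%. Simply deleting 10% of patients would give 0.2063/√0.90 = 0.217, below 0.2353. A loss larger than outright deletion comes from the imputation step, a separate matter.

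It is also true that no difference between arms and no type I error problem is shown, and that completing the diary away from the clinic is inferred from its being daily. None of this gives recorded entries a route into the analysis when the visit is missed.

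**Conclusion.** The point holds for missed visits. Postbaseline diary scores, including a multiplicity-controlled endpoint, are tied only to the visit date, so valid entries around the target day are replaced by imputation or by an unscheduled visit at any distance. This is a choice of method that can be improved, not merely a missing detail.

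The benefit is modest: about 1-3% in the standard error against direct MMRM, assuming 3-10% of Week 52 visits were missed with usable diaries and a between-visit correlation near 0.7. It is 0.4-3.9% if that correlation lies anywhere from 0.5 to 0.85. The actual size cannot be derived from the SAP. The stronger reasons for the change are that it avoids an unneeded missing-data assumption and gives one unambiguous derivation. The baseline diary value and visits within ±4 days raise no issue.

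**What to change.** Add to Section 6.3 and to the diary rows of Table JAIA.6.4: if a scheduled visit is missed, the diary score is the mean of the 7 days before the target study day (Days 358-364 for Week 52) when at least 4 entries exist, subject to the intercurrent-event and off-drug rules of Table JAIA.6.5. State that for diary scores this takes precedence over the unscheduled-visit mapping, and that imputation applies only when fewer than 4 entries exist. Use the same rule for every diary score.

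For a delayed Visit 16, keep the visit-date rule. At most, add a supplementary analysis anchored on Day 365.

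The cost is a sentence or two and a small derivation change on data already collected, with no effect on sample size or alpha. The drawback is that for these patients the diary score is no longer tied to a clinic visit. The change belongs before unblinding; after that it should be run only as a supplementary analysis.
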